^c Re-assessment of subject's response to efavaleukin alfa treatment will be conducted every 6 months and a decision may be made by the Sponsor, following discussion and agreement between the principal investigator and medical monitor, to allow subjects who wish to, to continue treatment through week 258 (Q2W dose) or week 259 (QW dose).

^d A single ECG will be collected prior to blood draws or other invasive procedures. See Section [9.2.3.3](#).

^e Record steroid use and/or changes to dose on concomitant medication CRF page.

^f A 2 or 6 minute walk test is optional for the NIH Form A assessment.

^g PFTs (spirometry) will be used in the NIH Form A assessment unless the subject is unable to comply. PFTs must be obtained at the Baseline visit unless they were performed at the Screening visit. Thereafter PFTs are strongly preferred at all visits which include the NIH Form A assessment and must be performed for all subjects who have an abnormal PFT at Baseline, who have known pulmonary GVHD or who have new pulmonary symptoms. If PFTs cannot be performed as part of the NIH Form A assessment, the lung symptom score should be substituted.

For women of childbearing potential, on study pregnancy tests are urine.

^h Doses of investigational product in phase 1b must be given within \pm 3 days from the scheduled visit for subjects in Q2W dosing and \pm 2 days from the scheduled visit for QW dosing. Subjects will remain at the site for at least 30 minutes following doses of investigational product. Once [REDACTED] has been selected, investigational product will be administered within \pm 2 days.

Table 2-5. Phase 1b Schedule of Activities – Extended Dosing Period Subjects Only (Week 159 Through Week 222)

	Visits for weekly dosing	TREATMENT PERIOD ^a																									PD Visit	SFU/ EOS ^b			
		Visits for weekly and biweekly dosing																													
Study Week	159,161,163,165, 167,169,171,173, 175,177,179,181, 183,185,187,189, 191,193,195,197, 197,199,201,203, 205,207,209,221	160	162	164	166	168	170	172	174	176	178	180	182 ^c	184	186	188	190	192	194	196	198	200	202	204	206	208 ^c	210	222	Any-time		
GENERAL ASSESSMENTS																															
Physical Examination																														X	
Vital Signs	X	X	X	X	X	X	X	X	X	X	X	X	X	X	X	X	X	X	X	X	X	X	X	X	X	X	X	X	X		
Weight																		X											X		
ECG ^d																		X											X	X	
CLINICAL OUTCOME ASSESSMENTS																															

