^c Re-assessment of subject's response to efavaleukin alfa treatment will be conducted every 6 months and a decision may be made by the Sponsor, following discussion and agreement between the principal investigator and medical monitor, to allow subjects who wish to, to continue treatment through week 258 (Q2W dose) or week 259 (QW dose).

^d A single ECG will be collected prior to blood draws or other invasive procedures. See [Section 9.2.3.3](#).

^e Record steroid use and/or changes to dose on concomitant medication CRF page.

^f A 2 or 6 minute walk test is optional for the NIH Form A assessment.

^g PFTs (spirometry) will be used in the NIH Form A assessment unless the subject is unable to comply. PFTs must be obtained at the Baseline visit unless they were performed at the Screening visit. Thereafter PFTs are strongly preferred at all visits which include the NIH Form A assessment and must be performed for all subjects who have an abnormal PFT at Baseline, who have known pulmonary GVHD or who have new pulmonary symptoms. If PFTs

[REDACTED]
For women of childbearing potential, on study pregnancy tests are urine.

[REDACTED]
e
scheduled visit for QW dosing. Subjects will remain at the site for at least 30 minutes following doses of investigational product. Once [REDACTED] has been selected, investigational product will be administered within \pm 2 days.

Table 2-6. Phase 1b Schedule of Activities – Extended Dosing Period Subjects Only (Week 223 Through Week 260)

	Visits for weekly dosing	TREATMENT PERIOD ^a																				PD Visit	SFU/ EOS ^b		
		Visits for weekly and biweekly dosing																							
Study Week	223,225,227,229, 231,233,235,237, 239,241,243,245, 247,249,251,253, 257,259	224	226	228	230	232	234 ^c	236	240	242	244	246	248	250	252	254	256	258	260/ EOET ^d	Any-time					
GENERAL ASSESSMENTS																									
Physical Examination																									
Vital Signs	X	X	X	X	X	X	X	X	X	X	X	X	X	X	X	X	X	X	X	X	X	X	X		
Weight							X														X	X			
ECG ^e							X														X	X	X		
Concomitant Medication	X	X	X	X	X	X	X	X	X	X	X	X	X	X	X	X	X	X	X	X	X	X	X		
Corticosteroid use ^f	X	X	X	X	X	X	X	X	X	X	X	X	X	X	X	X	X	X	X	X	X	X	X		
Adverse Events	X	X	X	X	X	X	X	X	X	X	X	X	X	X	X	X	X	X	X	X	X	X	X		
Serious Adverse Events	X	X	X	X	X	X	X	X	X	X	X	X	X	X	X	X	X	X	X	X	X	X	X		
Disease-Related Events	X	X	X	X	X	X	X	X	X	X	X	X	X	X	X	X	X	X	X	X	X	X	X		
NIH cGVHD Response Assessment (NIH Form A) ^g							X														X	X			

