5.1.1 Phase 1b

The phase 1b part of this study will be conducted as a multiple ascending dose (MAD) study. Each dosing cohort will consist of between 3 and 6 DLT-evaluable subjects who will receive efavaleukin alfa SC either QW or Q2W plus protocol permitted background therapy for 52 weeks. The DLT evaluation period is 4 weeks after the first dose of study drug. At the discretion of the Sponsor, following discussion and agreement between the principal investigator and medical monitor, subjects responding to efavaleukin alfa (as assessed by the end of week 50), who wish to continue treatment, may continue to receive efavaleukin alfa treatment at their current dosing regimen for up to an additional 52 weeks. The remaining subjects will complete the week 52/EOT visit. All subjects who continue to receive efavaleukin alfa during the extended dosing period will be reevaluated at week 76 for their response to treatment. Following discussion and agreement between the principal investigator and medical monitor, the Sponsor may decide to allow these subjects to continue treatment through week 102 (Q2W dose) or week 103 (QW dose). Subjects participating in extended dosing **through week 104** will complete the week 104/end of extended treatment (EOET) visit (see [Table 2-3](#)). **At the discretion of the Sponsor, following discussion and agreement between the principal investigator and medical monitor, subjects responding to efavaleukin alfa (as assessed by the end of week 104), who wish to continue treatment beyond week 104, may continue to receive efavaleukin alfa treatment at their current dosing regimen for up to an additional 156 weeks. Only subjects who are deemed eligible to continue extending dosing beyond week 102 or week 103 will complete**

dosing at week 104. The remaining subjects will complete the week 104/EOET visit. All subjects who continue to receive efavaleukin alfa during the extended dosing period will be reevaluated every 6 months for their response to treatment. Following discussion and agreement between the principal investigator and medical monitor, the Sponsor may decide to allow these subjects to continue treatment through week 258 (Q2W dose) or week 259 (QW dose). Subjects participating in extended dosing through week 258 or 259 will complete the week 260/EOET visit (see [Table 2-6](#)). All subjects will complete the 6-week safety follow-up after the last dose of efavaleukin alfa.

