8.3 Lost to Follow-up

A subject will be considered lost to follow-up if he or she repeatedly fails to return for scheduled visits and is unable to be contacted by the study site.

The following actions must be taken if a subject fails to return to the clinic for a required study visit:

- The site must attempt to contact the subject and reschedule the missed visit as soon as possible and counsel the subject on the importance of maintaining the assigned visit schedule and ascertain whether or not the subject wishes to and/or is able to continue in the study.
- In cases in which the subject is deemed lost to follow-up, the investigator or designee must make every effort to regain contact with the subject (where possible, 3 telephone calls and, if necessary, a certified letter to the subject's last known mailing address or local equivalent methods). These contact attempts are to be documented in the subject's medical record.
- If the subject continues to be unreachable, he/she will be considered to have withdrawn from the study with a primary reason of lost to follow-up.

- For subjects who are lost to follow-up, the investigator can search publicly available records [where permitted]) to ascertain survival status. This ensures that the data set(s) produced as an outcome of the study is/are as comprehensive as possible.

9. Study Assessments and Procedures

Study procedures and their time points are summarized in the Schedule of Activities (see [Table 2-1](#), [Table 2-2](#), [Table 2-3](#), [Table 2-4](#), [Table 2-5](#), [Table 2-6](#), [Table 2-7](#), and [Table 2-8](#)).

As protocol waivers or exemptions are not allowed if an enrolled subject is subsequently determined to be ineligible for the study, this must be discussed with the sponsor immediately upon occurrence or awareness to determine if the subject is to continue or discontinue study treatment.

Adherence to the study design requirements, including those specified in the Schedule of Activities, is essential and required for study conduct.

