### Vitals

Analysis Visit	Target Day	Study Day Window
----------------	------------	------------------

Week 1, Day 2	2	2
Week 1, Day 3	3	3
Week 1, Day 4	4	4-6
Week 1, Day 8	8	7-9
Week 1, Day 11	11	10-12
Week n, Day 7*n+1  (n = 2, 3, 4, 5, 6, 7, 8, 9, 10, 11, 12, 13, 14)	7n+1	Target day -2, Target day +4
Week 15, Day 106	106	104, Day 113-3
Week 16, Day 113 Pre-dose	113	Day 113-2, Day 113
Week 16, Day 114	114	Day 113 + 1
Week 16, Day 115	115	Day 113 + 2
Week 16, Day 116	116	Day 113 + 3
Week 17, Day 120	120	Day 113 + 4, 124
Week 18, Day 127	127	125-131
Week 20, Day 141	141	132-148
Week n, Day 7*n+1  (n = 22, 24, 26,.. to 258 in increments of 2)	7n+1	Target day -6, Target day +7
Week 260, Day 1821	1821	>1814

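### Tables 2-5 and 2-6 list no visit or dose for weeks 211-220, 238 and 255, although the protocol text provides for QW or Q2W treatment through week 258/259 with no planned break

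*Protocol*

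**What the plan says.** **Schedule tables (Protocol 2.2).** Table 2-5 is titled "Extended Dosing Period Subjects Only (Week 159 Through Week 222". Its list of QW-only weeks ends "205,207,209,221", and its columns shared by both regimens end "210 222 Any-time". Week 197 is printed twice. Table 2-6 is titled "Extended Dosing Period Subjects Only (Week 223 Through Week 260". Its QW-only list ends "247,249,251,253, 257,259", and its shared columns go from 236 to 240. In each table the same lists appear on both pages, including the page that carries the dosing rows.

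**Treatment text.** Protocol 5.1.1 allows up to 156 further weeks after week 104 at the subject's current regimen, and the sponsor may let subjects "continue treatment through week 258 (Q2W dose) or week 259 (QW dose"). Table 7-1 has weekly or biweekly dosing for the duration of the study. SAP 3.1 repeats the duration. No section describes a pause.

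**Status of the schedule.** The opening of Protocol Section 9 says: "Adherence to the study design requirements, including those specified in the Schedule of Activities, is essential and required for study conduct".

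**Visits tied to the schedule.** Under Protocol 9.1.4, a subject who stops after week 104 has the EOET visit within 7 days either side of the next regularly scheduled visit after the last dose. Under 9.1.5, safety follow-up is 6 weeks (± 3 days) after the last dose.

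**SAP windows.** Appendix G defines vital-sign windows from week 22 "to 258 in increments of 2". From week 110 it uses the same two-week step for chemistry, hematology and weight, for pharmacodynamics (PD) and for antibodies. It also says that only visits in the protocol's Schedule of Activities are considered for a given assessment.

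**The concern.** A site working from the tables finds no dose, vital signs or other visit for ten consecutive weeks, and then two further isolated gaps. A site working from Section 5.1.1 finds treatment continuing. Both are operative text, and nothing says which governs. In addition, the EOET visit is anchored to the next listed visit, so a hole in the list moves that visit. At analysis, Appendix G has windows in the hole but defers to a schedule that lists nothing there.

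**Working it through.** **1. End point.** 104 + 156 = 260, which matches the week 260/EOET visit. The stated duration is therefore consistent; the problem is the list of weeks leading up to it.

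**2. Dosing weeks implied by the text after week 104.**
- QW, weeks 105 to 259: 259 − 105 + 1 = 155.
- Q2W, even weeks 106 to 258: (258 − 106)/2 + 1 = 77.

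**3. Dosing weeks listed.** The duplicate 197 is counted once, and week 260 is left out because the text ends dosing at 258/259.

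| Table | Odd weeks | Even weeks |
|---|---|---|
| 2-4 | 27 | 27 |
| 2-5 | 27 | 27 |
| 2-6 | 18 | 17 |
| Total | 72 | 71 |

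- QW: 72 + 71 = 143 listed; 155 − 143 = 12 absent (211 to 220, 238, 255).
- Q2W: 71 listed; 77 − 71 = 6 absent (212, 214, 216, 218, 220, 238).

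**4. Longest interval between listed doses.**
- QW: 221 − 210 = 11 weeks.
- Q2W: 222 − 210 = 12 weeks.
- The other gaps are 2 weeks for QW (237 to 239, 254 to 256) and 4 weeks for Q2W (236 to 240).

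**5. EOET against safety follow-up, last dose at week 210.**
- Safety follow-up: 210 + 6 = week 216, ± 3 days.
- EOET, QW: next listed visit is week 221, so no earlier than 11 × 7 − 7 = 70 days after the last dose.
- EOET, Q2W: next listed visit is week 222, so no earlier than 12 × 7 − 7 = 77 days.
- Latest safety follow-up: 6 × 7 + 3 = 45 days.
- EOET therefore follows the safety follow-up/end-of-study visit by at least 70 − 45 = 25 days (QW) or 77 − 45 = 32 days (Q2W).
- Both 70 and 77 days exceed the SAP 9.7.1.2 limits of 9 days (QW) and 16 days (Q2W), so PD data from that EOET visit would be excluded.

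**6. Appendix G windows with no listed visit.** The target day is 7n + 1 and the window runs from −6 to +7 days.
- Weeks 212 to 220: targets 1485 to 1541, windows covering days 1479 to 1548.
- Week 238: target 1667, window days 1661 to 1674.
- Week 255 is odd and has no window of its own.

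**7. Could renumbering alone explain it?** Table 2-5 has 27 even columns; counted continuously from 160 they would end at 212, not 222. If the last odd and even entries were meant as 211 and 212, weeks 213 to 222 would then be unlisted, because Table 2-6 starts at 223. That is still ten weeks. The response re-assessment marks at 182, 208 and 234 are 26 weeks apart, which fits the six-monthly rule, so the unlisted weeks are real calendar time.

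**The case against.** The strongest reply is that this is a clerical slip with little practical reach. Much of that stands. The duplicated 197 and the column count point to a listing error. The treatment text is consistent across the protocol and SAP. The Section 9 adherence statement covers study design requirements generally and does not rank the tables above Section 5.1.1. That sites would actually diverge is a possibility and has not been shown.

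A reader might infer more than the documents support:

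- *A deliberate ten-week treatment break.* No section describes one.
- *SAP Appendix G contradicts the tables.* It does not. It is a mapping grid restricted to Schedule of Activities visits. For example, it has two-weekly chemistry windows where the tables mark chemistry only occasionally. What remains is that windows exist at weeks 212 to 220 and 238 with no listed visit, so the handling of any data collected then is unclear.
- *Exposure and missed-dose rules are compromised.* Days on IP (SAP 5.4) is last dose date minus first dose date plus 1, so an internal gap does not change it; only total dose could differ. The visible text has no missed-dose rule beyond the PD exclusion. PD sampling in this period is sparse, so that effect is small.
- *Primary safety data are at risk.* DLTs are confined to the first 4 weeks. Adverse events are reportable from first dose through safety follow-up (Protocol 9.2.3.1.1.2), whatever visits are listed.

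Early termination (SAP 1 and 3.1) also counts. Week 211 is reachable only by responders kept on at the sponsor's discretion. Protocol 5.4 reports dosing for up to 54 weeks as of 27 October 2020. A subject then at week 54 would need another 211 − 54 = 157 weeks, to about the end of October 2023. The documents give no termination date, so they do not settle whether anyone got there.

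**Conclusion.** The inconsistency is real and should be resolved. Read literally, Tables 2-5 and 2-6 omit 12 of 155 QW and 6 of 77 Q2W dosing weeks with their visits, and the EOET rule can place that visit after safety follow-up. A text-reading artefact is unlikely: each list is repeated on both pages of its table, and the odd and even lists in Table 2-5 break at the same place.

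The counts assume uninterrupted QW or Q2W dosing as the text describes; they do not establish that the text is right and the tables wrong. The practical effect is limited to long-term extension subjects and may be nil if none reached week 211.

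**What to change.** Reconcile Tables 2-5 and 2-6 with Section 5.1.1 into one list of visits and doses for weeks 159 to 260. State what applies in weeks 211 to 220, 238 and 255, and remove the duplicate 197. Confirm that the EOET rule then yields a workable visit order, and align the Appendix G windows to the agreed list. Which version is correct is for the sponsor to determine.

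Given early termination, a SAP statement may be enough: say whether any subject reached week 211 and, if so, how data from the unlisted weeks are mapped. If none did, one sentence closes the point.

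The cost is a clarification to two tables and a short SAP edit. No new data collection and no change to the DLT or adverse-event analyses is needed.

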3.1 Study Rationale

This open-label, multicenter, phase 1b/2 study is planned to evaluate the safety and efficacy of efavaleukin alfa (AMG 592) in subjects with steroid refractory chronic graft versus host disease (cGVHD). The phase 1b part of the study will evaluate the safety, pharmacokinetics (PK), and pharmacodynamics (PD) of efavaleukin alfa and will define the maximum tolerated dose (MTD) and/or a biologically optimal dose. [REDACTED]

[REDACTED]

3.2 Background

3.2.1 Disease

Chronic graft-versus-host disease (cGVHD) is a systemic inflammatory disorder that is associated with considerable morbidity and mortality and develops in more than half of long term survivors after hematopoietic stem-cell transplantation (HSCT) (Kahl, 2007). It is the most common long-term complication of allogeneic HSCT and the leading cause of [REDACTED]. The median time to onset is 4 to 6 months after HSCT but 5% to 10% of cases are diagnosed at greater than 1 year after HSCT (Lee and Flowers, 2008). Per 21 CFR 312.300, cGVHD meets the definition of a serious condition as it is a condition associated with morbidity that has a substantial impact on day to day function. Improved treatment for cGVHD is a major unmet need.

First line therapy for moderate to severe cGVHD consists of systemic glucocorticoid therapy or calcineurin inhibitors. Treatment with systemic glucocorticoids has limited efficacy, with half of patients requiring second-line therapy, and is associated with substantial long-term toxicity.

Second-line therapy for those who fail systemic glucocorticoids is not well established. Estimated response rates to experimental therapy are confounded by the lack of controlled trials and the non-standardized use of outcome measures. [REDACTED]

[REDACTED]

[REDACTED]

[REDACTED]

[REDACTED]. However, few multi-center controlled trials have replicated these high response rates. For instance, a recent multi-center randomized controlled phase 2 cross-over trial comparing imatinib versus rituximab for cutaneous sclerosis associated

with cGVHD reported a significant clinical response in 26% of patients in the imatinib arm versus 27% of subjects in the rituximab arm. Furthermore, only 17% of imatinib-treated subjects and 14% of rituximab-treated subjects achieved 'treatment success', defined as a significant clinical response without cross-over, relapse, or death (Arai et al, 2016).

With regard to the expected response rate with current standard of care (SOC), few studies include an SOC arm for comparison. The largest relevant study (n = 151 evaluable patients), a double-blind, randomized controlled trial comparing mycophenolate mofetil (MMF) plus SOC versus SOC alone, demonstrated that only 18% in the SOC arm versus 23% in the MMF plus SOC met the primary endpoint of complete withdrawal of systemic immunosuppressant therapy after 2 years (p = NS) (Martin, 2009). A study of Extra Corporeal Photophoresis (ECP) versus SOC reported a blinded evaluation of the Total Skin Score of 8.5% in the SOC arm versus 14.5% in the ECP arm (Flowers, 2008).

There is currently 1 approved, commercially available drug in the US and Canada for the treatment of patients with steroid-refractory cGVHD. Ibrutinib, an inhibitor of Bruton's tyrosine kinase (BTK), was approved in 2017 for the treatment of adults with cGVHD after failure of 1 or more lines of systemic therapy. [REDACTED]

[REDACTED]

[REDACTED]

[REDACTED]

The pathogenesis of cGVHD is complex and incompletely understood. It is characterized by aberrant negative selection of autoreactive T cells due to thymic dysfunction, autoantibody production, and fibrotic injury (Cutler et al, 2017; MacDonald et al, 2017; Soci and Ritz, 2014; Blazar et al, 2012).

Regulatory T cells (Treg) are a subset of cluster of differentiation (CD)4 T cells that suppress inflammation and whose numbers and function are maintained by interleukin-2 (IL-2). A loss in the homeostatic balance between Treg and other lymphocytes is considered a causative factor in many inflammatory conditions, including cGVHD. Low dose IL-2 and recombinant IL-2 (Proleukin® [aldesleukin]) have been studied in active cGVHD subjects (Koreth et al, 2016; Koreth et al, 2011). Disease improvement has generally been associated with sustained Treg expansion *in vivo* without increases in rates of infection or cancer relapse. However, the narrow window between adequate Treg enrichment and side effects (nausea, fever, fatigue) due to stimulation of T effector

cells (Teff) and natural killer (NK) cells may limit achievement of optimal Treg expansion (Koreth et al, 2011). Notably, a dose of 3×10^6 IU/m² induced persistent National Cancer Institute Common Terminology Criteria for Adverse Events (NCI CTCAE version 4.03) grade 1 constitutional symptoms (fever, malaise, and arthralgia), necessitating a 50% dose reduction, and indicating a narrow therapeutic window between adequate Treg enrichment and stimulation of effector cells (Koreth et al, 2011).

3.2.2 Amgen Investigational Product Background: Efavaleukin Alfa

Efavaleukin alfa is an Fc IL-2 mutein fusion protein designed to increase Treg selectivity, which has been developed to expand Tregs in subjects with inflammatory diseases (refer to the Investigator's Brochure). Interleukin-2 is a key growth factor for Tregs and is essential for Treg development, homeostasis and function. At low dose IL-2 binds preferentially to the α subunit (CD25) of the high-affinity IL-2 receptor which is expressed constitutively by Tregs and is absent on naive Tcells and unactivated T memory cells. This results in selective activation of Tregs. However, at higher doses IL-2 also activates other immune cells such as CD4+ and CD8+ T effector cells, NK cells and natural killer T cells (NKT) via the dimeric low affinity IL-2 receptor. Compared with aldesleukin, efavaleukin alfa exhibits greatly improved selectivity for Tregs over Teff and NK cells both in vitro and in vivo, potentially resulting in an improved therapeutic margin. In addition, the Fc domain of efavaleukin alfa provides a prolonged half-life compared with aldesleukin, thus reducing dosing frequency to maintain Treg enrichment. Treatment in subjects with steroid-refractory cGVHD with efavaleukin alfa is anticipated to provide greater sustained Treg expansion and an improved safety profile, leading to greater efficacy and tolerability.

A detailed description of the chemistry, pharmacology, efficacy, and safety of efavaleukin alfa is provided in the Investigator's Brochure.

